4.7.3 Additional safety assessments

4.7.3.1 Laboratory variables, vital signs, and electrocardiograms

The following laboratory variables, vital signs, and electrocardiogram (ECG) variables will be analyzed. They will be converted into International System of Units (SI) unless otherwise specified.

• Hematology:

- Red blood cells (RBC) and platelets: RBC, Hemoglobin, Hematocrit, Mean Cell Volume (MCV)*, Mean Corpuscular Hemoglobin (MCH)*, Mean Corpuscular Hgb Concentration (MCHC)*, Mean Platelet Volume (MPV)*, Red cell distribution width (RDW)*, Reticulocyte
- White blood cell (WBC) count with differential: WBC, Neutrophils, Lymphocytes, Monocytes, Eosinophils, Basophils
- Coagulation: prothrombin time/International Normalized Ratio (INR) and activated partial thromboplastin time (aPTT)
- Serum chemistry:
 - Metabolism: Glucose, Creatinine phosphokinase (CPK)
 - Electrolytes: Sodium, Chloride, Calcium, Phosphorus, Potassium
 - Renal function: Creatinine, Blood Urea Nitrogen (BUN)
 - Liver function: Aspartate aminotransferase (AST), Alanine aminotransferase (ALT), Total bilirubin, Direct bilirubin, Indirect bilirubin, Alkaline phosphatase (ALP), Albumin, Total Protein

b Bleeding events is identified by narrow search of SMQ = Haemorrhages

c Infection identified by primary SOC = "Infections and infestations"

- Thrombopoietin (TPO) levels
- Urinalysis*: Specific gravity, pH, glucose, protein, blood, ketones, bilirubin, urobilinogen, nitrite, leukocyte esterase
- Vital signs: blood pressures (BP), pulse, temperature* and respiratory rate* and body weight, height*
- ECG variables: pulse rate*, QT interval*, PR interval, RR interval*, QRS duration, QTcF interval and overall ECG assessments (normal, abnormal not clinically significant and abnormal clinically significant)
- Immunoglobulins: Immunoglobulin G, Immunoglobulin M, Immunoglobulin E (IgE), Immunoglobulin G Subclass 1, Immunoglobulin G Subclass 4
- Hemolysis Panel: Direct Coombs (Anti-Human Globulin), Haptoglobin

For descriptive summary, data below the lower limit of quantitation/detection limit (LLOQ) will be replaced by half of the LLOQ, data above the upper limit of quantification will be replaced by ULOQ value.

Quantitative analyses

For all laboratory variables, vital signs, and ECG variables above, descriptive statistics for results and change from baseline will be provided for each planned visit, including the last value during the on-treatment period. These analyses will be performed using central measurements (when available) for laboratory variables and using local measurements for ECG variables.

Analyses according to PCSA

Potentially clinically significant abnormality (PCSA) analyses will be performed based on the PCSA list currently in effect at Sanofi at the time of the database lock (Section 5.4). For parameters for which no PCSA criteria are defined, similar analyses will be done using the normal range, if applicable. For parameters defined as efficacy endpoints, PCSA or PCSA similar summaries will not be provided.

Analyses according to PCSA will be performed based on the worst value during the treatment-emergent period, using all measurements (either local or central, either scheduled, nonscheduled or repeated). For laboratory variables, vital signs, and ECG variables above, the incidence of participants with at least one PCSA during the treatment-emergent period will be summarized regardless of the baseline level and according to the following baseline status categories:

- Normal/missing
- Abnormal according to PCSA criterion or criteria

^{*} Only PCSA or PCSA similar tables will be provided.

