# Part B

Clinical laboratory results will be summarized descriptively for baseline and each monthly clinic visit. The numerical change from baseline to each visit will be computed. Laboratory shift tables will be provided for all laboratory parameters where low/normal/high or abnormal/normal status can be ascertained for shift from baseline to each monthly clinic visit. Listings of individual laboratory parameters by visit with normal ranges and abnormality assessments will also be completed by patient.

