# 11.5.1 Laboratory and ECG Abnormalities

Laboratory test results will be recorded on the laboratory results pages of the CRF or merged electronically with the CRF data, and will appear on electronically produced laboratory reports provided to the Investigator. Data will be reported to Principal Investigators in laboratory reports and merged with CRF data on the back end. Some laboratory data may be manually entered, if necessary.

Any treatment-emergent abnormal laboratory or ECG result that is clinically significant (ie, meeting one or more of the following conditions) should be recorded as a single diagnosis on the AE page in the CRF:

- Accompanied by clinical symptoms
- Leading to a change in study drug (eg, dose modification, interruption, or permanent discontinuation)
- Requiring a change in concomitant therapy (eg, addition of, interruption of, discontinuation of, or any other change in a concomitant medication, therapy, or treatment)

Note: Any laboratory or ECG result abnormality fulfilling the criteria for an SAE must be reported as such, in addition to being recorded as an AE in the CRF.

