# 16.4 Appendix 4: Schedule of Assessments (Part B)

			Activ	ve Treatment Po	eriod for 24 We	eks and 4 Weel	k Follow Up Pe	eriod 			
	Screening (D-28 to D-1)	Enrolment Week 1 SD1	Week 5 SD29	Week 9 SD57	Week 13 SD85	Week 17 SD113	Week 21 SD141	Last Day of Treatment Week 25 SD169	End of Study SD197 / 4 weeks post last dose	Weekly Lab Visits Between Clinic Visits	Early Withdrawal/ Unscheduled visit
Informed Consent	X										
Inclusion/Exclusion Criteria	X	X1									
AEs	X	X	X	X	X	X	X	X	X		X
Concomitant Medications	X	X	X	X	X	X	X	X	X		X
Height	X										
Weight	X	X	X	X	X	X	X	X	X		X
Physical exam/med history 	X	X	X	X	X	X	X	X	X		X
ECG (12-lead, single)	X	X	X	X	X	X	X	X	X		X
Vital Signs	X	X	X	X	X	X	X	X	X		X
Urinalysis	X	X	X	X	X	X	X	X	X		X
Hep B & C, HIV 	X										
Pregnancy test 	X	X	X	X	X	X	X	X	X		X
FSH 	X										
ABO and Rh Blood Type 	X										
Serum Chemistry	X	X	X	X	X	X	X	X	X		X
Hematology, differential, reticulocytes	X	X	X	X	X	X	X	X	X	X	X
PT/INR PTT	X	X	X	X	X	X	X	X	X		
TPO levels	1	X	X	X	X	X	X	X	X		
Hemolysis panel 	1	X	X	X	X	X	X	X	X		
Mean platelet volume 		X	X	X	X	X	X	X	X		
Immature platelet fraction 				12							
1					·						
BTK Occupancy 		X	X	X				X			
PK sample 		X	X	X							

			Active Treatment Period for 24 Weeks and 4 Week Follow Up Period 								
	Screening (D-28 to D-1)	Enrolment Week 1 SD1	Week 5 SD29	Week 9 SD57	Week 13 SD85	Week 17 SD113	Week 21 SD141	Last Day of Treatment Week 25 SD169	End of Study SD197 / 4 weeks post last dose	Weekly Lab Visits Between Clinic Visits 1	Early Withdrawal/ Unscheduled visit
QOL Questionnaires 	X	X	X	X	X	X	X	X	X		
IBLS	X	X	X	X	X	X	X	X	X		X

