5.3 APPENDIX 3 DATA HANDLING CONVENTIONS

Platelet count assessments

For efficacy analyses using weekly platelet counts, the use of local platelet count will be prioritized, central platelet count will be used only when local is missing; the use of scheduled visit will be prioritized, and unscheduled visit will be used when scheduled is missing. If a weekly (starting from week 2) scheduled platelet count is missing, then an unscheduled platelet count will be allocated to the corresponding visit. See Table 6 for details.

Analysis windows for time points

The following analysis windows will decide how the scheduled and/or unscheduled visits will be used in the by-visit analyses of efficacy, safety, and participant reported outcome variables.

Platelet counts conducted locally will be used for the efficacy analyses. Platelet counts conducted centrally at Clinic Visits will be used as a back-up for missed or non-analyzable local lab samples.

A scheduled measurement will be used if it is available. Otherwise, an unscheduled measurement (including early withdrawal visit) will be allocated to a scheduled visit if it is within the analysis window of the scheduled visit. After applying these time windows, if multiple assessments are associated to the same time point, the closest from the targeted study day will be used. If the difference is a tie, the value after the targeted study day will be used. If multiple valid values exist within a same day, then the first value of the day will be selected.

If there is no measurement for a given parameter in an analysis window, data will be considered missing for the corresponding visit.

28-Nov-2022 Version number: 1

Table 6 - Analyses window definition

Scheduled visit post baseline	Targeted study day (Analysis window) – Platelet count only	Targeted study day (Analysis window) – Other ^a
Week 1 to LTE Month 6		
Week n ^b	1+7*(n-1) (+/-3)	
Week 5	29 (+/-3)	29 (-13,+14)
Week 9	57 (+/-3)	57 (-13,+14)
Week 13	85 (+/-3)	85 (-13,+14)
Week 17	113 (+/-3)	113 (-13,+14)
Week 21	141 (+/-3)	141 (-13,+14)
Week 25/ C1D1_LTE	169 (+/-3)	169 (-13,+14)
C1D8_LTE	176 (+/-3)	
C1D15_LTE	183 (+/-3)	
C1D22_LTE	190 (+/-3)	
C2D1_LTE	197 (+/-3)	197 (-13,+14)
C2D8_LTE	204 (+/-3)	
C2D15_LTE	211 (+/-3)	
C2D22_LTE	218 (+/-3)	
C3D1_LTE	225 (+/-3)	225 (-13,+14)
C3D8_LTE	232 (+/-3)	
C3D15_LTE	239 (+/-3)	
C3D22_LTE	246 (+/-3)	
C4D1_LTE	253 (+/-3)	253 (-13,+14)
C4D8_LTE	260 (+/-3)	
C4D15_LTE	267 (+/-3)	
C4D22_LTE	274 (+/-3)	

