(mL/min/1.73m2) (Estimate of GFR based on an MDRD equation)	≥15 - <30 (severe decrease in GFR) ≥30 - < 60 (moderate decrease in GFR) ≥60 - <90 (mild decrease in GFR) ≥ 90 (normal GFR)	Pharmacokinetics in patients with impaired renal function-study design, data analysis, and impact on dosing and labeling

Parameter	PCSA	Comments
Creatinine	≥150 µmol/L (Adults) ≥30% change from baseline ≥100% change from baseline	Benichou C., 1994.
Uric Acid Hyperuricemia Hypouricemia	>408 µmol/L <120 µmol/L	Harrison- Principles of internal Medicine 17 th Ed., 2008.
Blood Urea Nitroge	en ≥17 mmol/L	
Chloride	<80 mmol/L >115 mmol/L	
Sodium	≤129 mmol/L ≥160 mmol/L	
Potassium	<3 mmol/L ≥5.5 mmol/L	FDA Feb 2005.
Total Cholesterol	≥7.74 mmol/L	Threshold for therapeutic intervention.
Triglycerides	≥4.6 mmol/L	Threshold for therapeutic intervention.
Lipasemia	≥3 ULN	
Amylasemia	≥3 ULN	
Glucose Hypoglycaemia Hyperglycaemia	≤3.9 mmol/L and <lln ≥11.1 mmol/L (unfasted); ≥7 mmol/L (fasted)</lln 	ADA May 2005. ADA Jan 2008.
HbA1c	>8%	
Albumin	≤25 g/L	
CRP	>2 ULN or >10 mg/L (if ULN not provided)	FDA Sept 2005.
Hematology		
WBC	<3.0 Giga/L (Non-Black); <2.0 Giga/L (Black) ≥16.0 Giga/L	Increase in WBC: not relevant. To be interpreted only if no differential count available.
Lymphocytes	>4.0 Giga/L	
Neutrophils	<1.5 Giga/L (Non-Black); <1.0 Giga/L (Black)	International Consensus meeting on drug-induced blood cytopenias, 1991. FDA criteria.
Monocytes	>0.7 Giga/L	
Basophils	>0.1 Giga/L	
Eosinophils	>0.5 Giga/L or >ULN (if ULN≥0.5 Giga/L)	Harrison- Principles of internal Medicine 17th Ed., 2008.

Parameter	PCSA	Comments
Hemoglobin	≤115 g/L (Male); ≤95 g/L (Female) ≥185 g/L (Male); ≥165 g/L (Female)	Criteria based upon decrease from baseline are more relevant than based on absolute value. Other categories for decrease from baseline can be used
	Decrease from Baseline ≥20 g/L	(≥30 g/L, ≥40 g/L, ≥50 g/L).
Hematocrit	≤0.37 v/v (Male); ≤0.32 v/v (Female) ≥0.55 v/v (Male); ≥0.5 v/v (Female)	
RBC	≥6 Tera/L	Unless specifically required for particular drug development, the analysis is redundant with that of Hb. Otherwise, consider FDA criteria.
Platelets	<100 Giga/L ≥700 Giga/L	International Consensus meeting on drug-induced blood cytopenias, 1991.
Urinalysis		
pH	≤4.6 ≥8	
Vital signs		
HR	≤50 bpm and decrease from baseline ≥20 bpm ≥120 bpm and increase from baseline≥20 bpm	To be applied for all positions (including missing) except STANDING.

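### The worst-value abnormality analysis in SAP Part B does not count participants whose lymphocytes fall below normal, and the SAP defines no other table that does

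*SAP*

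**What the plan says.** SAP Part B 4.7.3.1 lists lymphocytes among the haematology variables to be analysed. It plans two kinds of output: by-visit descriptive statistics, including the last on-treatment value, and a count of participants with at least one PCSA. The PCSA count takes the worst treatment-emergent value from all measurements, scheduled or not, local or central, and is split by baseline status. The rule for parameters without a threshold is: "For parameters for which no PCSA criteria are defined, similar analyses will be done using the normal range, if applicable".

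In Appendix 4 (section 5.4), the lymphocyte row has a single criterion, above 4.0 Giga/L. The list to be applied is the sponsor's list in effect at database lock; Appendix 4 is the printed version.

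Protocol 10.10.2 makes two promises for Part B. The first, for baseline against each monthly clinic visit, is: "Laboratory shift tables will be provided for all laboratory parameters where low/normal/high or abnormal/normal status can be ascertained". The second is: "Listings of individual laboratory parameters by visit with normal ranges and abnormality assessments will also be completed by patient". SAP Part B Appendix 3 (section 5.3) says that unscheduled values feed safety shift summaries where applicable, but section 4.7.3.1 defines none. Protocol 10.12 says that the SAP supersedes the protocol's statistical methods.

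**The concern.** The PCSA analysis is the one Part B laboratory table that uses every measurement and reports a number of participants. For lymphocytes it looks only upwards. The drug inhibits B-cell activation (Protocol 1.1), and SAP 4.7.2 tabulates infections of Grade 2 or higher separately, so a fall in lymphocytes is a reasonable thing for a reader to look for.

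Characterising safety at 400 mg BID is a primary Part B objective (SAP Part B 1.2). SAP Part A 5.5.6 plans out-of-normal-range shift tables and a summary of post-baseline minimum values. A fall at the same dose would therefore be tabulated in Part A, while its tabulation in Part B depends on a protocol table that the SAP does not define.

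**Working it through.** The plan gives no figure to reproduce here, so the check sets the texts side by side.

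**1. Does the fallback apply to lymphocytes?** The condition in 4.7.3.1 is that no PCSA criterion is defined for the parameter. Appendix 4 defines one (above 4.0 Giga/L), so the condition fails. There are 0 low-side lymphocyte criteria in the printed list, so the PCSA table counts high values only.

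**2. Does another row stand in?** The printed criteria for the white-cell variables are:

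| Variable | Low side | High side |
|---|---|---|
| Total WBC | yes | yes |
| Neutrophils | yes | no |
| Lymphocytes | no | yes |
| Monocytes, basophils, eosinophils | no | yes |

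Total WBC is no substitute. Its comment restricts interpretation to cases without a differential, and Part B collects one. The arithmetic also shows why: the low threshold for non-Black participants is 3.0 Giga/L, so anyone with neutrophils of 3.0 Giga/L or more cannot fall below it, however low the lymphocytes. Red cells are also high-side only, but their comment says that "the analysis is redundant with that of Hb", and haemoglobin has low criteria. Lymphocytes have no such partner.

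**3. How does the same rule treat a variable with no row?** The immunoglobulins in 4.7.3.1 have no row in Appendix 4, so the normal-range fallback does apply to them and low IgG or IgM is counted. Whether a low value is counted thus depends on whether the list happens to contain any row for that parameter.

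**4. Do the other outputs count low lymphocytes?**
- By-visit statistics give means, medians and minima, not numbers of participants below normal.
- Adverse event tables (SAP 4.7.2) capture a fall if it is recorded as an event. Protocol 11.5.1 requires that for "Any treatment-emergent abnormal laboratory or ECG result that is clinically significant", meaning one with symptoms or with a change in study drug or concomitant therapy. An asymptomatic fall without action need not be recorded.
- The listings in Protocol 10.10.2 show flagged values by patient but are not a table of counts.
- The shift tables in Protocol 10.10.2 would count a shift to low, but SAP Part B does not define them.

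**5. If the shift tables are produced, do they cover the same ground?** In Protocol Appendix 4, the row "Hematology, differential, reticulocytes" is marked at the monthly clinic visits and at the weekly laboratory visits between them. Weeks 2 to 25 give 24 scheduled post-baseline counts. The monthly visits are Weeks 5, 9, 13, 17, 21 and 25, which is 6. For assessments other than platelets, SAP Table 6 uses four-weekly windows, and "if multiple assessments are associated to the same time point, the closest from the targeted study day will be used". A weekly value can stand in for a missed monthly one, but it does not otherwise enter. A short fall that recovers before the next monthly visit can therefore be missed, whereas the worst-value analysis would use it.

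**The case against.** A reader might infer that no Part B table of any kind would count low lymphocytes. The documents do not support that. Protocol 10.10.2 specifies low/normal/high shift tables for every laboratory parameter where the status can be determined. SAP Appendix 3 presupposes shift summaries, and the SAP's version history declares no major changes to the analysis. Silence in 4.7.3.1 is not a withdrawal. What remains is that the tables' status is unclear, because the SAP supersedes the protocol's methods and does not define them.

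A reader might also infer that the missing low side is a drafting error, or that it hides a known risk. Neither can be shown. Four of the five differential cell types are high-side only in Appendix 4, which fits a deliberate sponsor-wide list, and the list at lock may differ from the printed one. The important potential risks in Protocol 2.2 are not visible in the public text, so nothing there shows that low lymphocytes are a concern for this drug.

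Finally, the safety endpoint refers to clinically significant laboratory changes, which Protocol 11.5.1 routes to the adverse event tables, and infections have their own tables. This stands and limits the importance of the gap: what goes uncounted is the asymptomatic fall that prompts no action.

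**Conclusion.** The point holds in limited form. On the printed list, the Part B worst-value analysis cannot count participants whose lymphocytes fall below normal. The only planned table that could count such falls from the laboratory data themselves is promised in the protocol, left undefined in the SAP and restricted to monthly visits.

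The gap is small: one direction of one parameter, in about 23 participants, with flagged listings promised and clinically significant cases captured as adverse events. The number of participants affected cannot be estimated from the documents. The conclusion assumes that the list at database lock keeps the printed lymphocyte row and that the fallback is applied by parameter, as worded. This is a desirable improvement to a descriptive safety analysis, not a defect that threatens a conclusion of the trial.

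**What to change.** In SAP Part B 4.7.3.1, add one lymphocyte row, below LLN, on the worst treatment-emergent value from all measurements, split by baseline status (normal or missing; abnormal) as for the other PCSA rows. Write it in 4.7.3.1 itself, because the list in Appendix 4 may be replaced at lock. Defining the Protocol 10.10.2 shift tables in the SAP would also settle their status, but they stop at monthly visits, so the added row is the better choice.

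If database lock has passed, label the output supplementary. The cost is one descriptive row beyond the sponsor-standard list, from data already collected, with no effect on any efficacy result.

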3.4.2 Analysis Period

There are primarily 3 analysis periods for safety analyses:

- 1) Main period is
 - Main on-treatment period + FU, if the patient did not enter LTE
 - Main on-treatment period only, if the patient entered LTE
- 2) LTE period is LTE on-treatment period + FU
- 3) Main and LTE period combined, if the patient entered LTEs

Efficacy analyses will be based on on-treatment period (i.e., up to end of treatment +1 day), with the exception of descriptive analyses which will include post-treatment follow up visits.

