3.4.4 Analysis Visits

In addition to study visits described above, analysis visits based on dosing cycle of each dose level will be derived for descriptive summary during the main treatment period as follows:

- 1st Cycle of Exposure: Day 1, Day 8, Day 15 and Day 22
- 2nd Cycle of Exposure: Day 1, Day 8, Day 15 and Day 22
- 3rd Cycle of Exposure: Day 1, Day 8, Day 15 and Day 22
- 4th Cycle of Exposure: Day 1, Day 8, Day 15 and Day 22
- 5th Cycle of Exposure: Day 1, Day 8, Day 15 and Day 22
- 6th Cycle of Exposure: Day 1, Day 8, Day 15 and Day 22
- Xth Cycle of Exposure: Day 1, Day 8, Day 15 and Day 22 for patients who had treatment cycle(s) beyond Cycle 6
- Last value on-treatment (Last post-baseline visit during the main on-treatment period including unscheduled visits within each dose level)

For example, if a patient received 200 mg QD at Cycle 1, 400 mg QD at Cycle 2 and Cycle 3 and 300 mg BID at Cycle 4 and Cycle 5, the scheduled visits will be mapped to the analysis visits as follows:

Dose Level	Scheduled Visit	Analysis Visit
200 mg QD	Cycle 1 – Day 1, 8, 15 and 22	200 mg QD: 1st Cycle of Exposure – Day 1, 8, 15 and 22
400 mg QD	Cycle 2 – Day 1, 8, 15 and 22	400 mg QD: 1st Cycle of Exposure – Day 1, 8, 15 and 22
400 mg QD	Cycle 3 – Day 1, 8, 15 and 22	400 mg QD: 2 nd Cycle of Exposure – Day 1, 8, 15 and 22
300 mg BID	Cycle 4 – Day 1, 8, 15 and 22	300 mg BID: 1 st Cycle of Exposure – Day 1, 8, 15 and 22
300 mg BID	Cycle 5 – Day 1, 8, 15 and 22	300 mg BID: 2 nd Cycle of Exposure – Day 1, 8, 15 and 22

Note: Visits occurred at and after the visit where dose reduction occurred will not be mapped.

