4.1 GENERAL CONSIDERATIONS

In general, continuous data will be summarized using the number of observations available, mean, standard deviation, median, (Q1, Q3 if applicable), minimum, and maximum. Categorical and ordinal data will be summarized using the count and percentage of participants.

The baseline value is defined as the last available value before the first dose of investigational medicinal product (IMP). For participants enrolled, however not treated, the baseline value is defined as the last available value before enrollment.

Baseline of platelet count is defined as the average of three platelet counts: two qualified screening platelet counts collected in eCRF and Week 1 (study day 1) platelet count.

Observation period

The observation period will be divided into 3 segments:

- The **pre-treatment period** is defined as the period up to date of first investigational medicinal product (IMP) administration.
- The **on-treatment period** is defined as the period from the first dose of IMP to the last dose of IMP + 1. The on-treatment period includes the main on-treatment period and the long-term extension (LTE) on-treatment period.
 - If the subject did not enter LTE, the **main on-treatment period** is defined as from the date of first dose of IMP to the date of the last dose of IMP + 1.
 - If the subject entered LTE, the **main on-treatment period** is defined as from the date of first dose of IMP to the date before the first dose of IMP during LTE. Date of first dose during LTE is based on the date of dosing reported on LTE Cycle 1 Day 1 (C1D1 LTE) in Study Drug Administration eCRF.
 - LTE on-treatment period is defined as from the date of first dose of IMP during LTE to the last dose of IMP + 1.
- The **post-treatment period** is defined as the period from the end of the on-treatment period.

The **treatment-emergent period** is any time after the first administration of rilzabrutinib. Treatment-emergent (TE) period includes both on-treatment period and post-treatment period. That is, **main treatment-emergent period** includes main on-treatment period and post-treatment period for those did not enter LTE; **LTE treatment-emergent period** includes LTE on-treatment period and post-treatment period.

Property of the Sanofi group - strictly confidential

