Analysis of all adverse events

The overview of TEAE with the details below will be generated:

- Any TEAE
- Any grade \geq 3 TEAE
- Any treatment emergent SAE
- Treatment emergent SAE related to IMP as per Investigator's judgment
- TEAE leading to death
- Grade 5 TEAE (any TEAE with a fatal outcome during the treatment-emergent period)
- Any TEAE leading to permanent IMP discontinuation
- TEAE related to IMP as per Investigator's judgment
- Bleeding events (Intensity Grade 2 or higher)
- Infection (Intensity Grade 2 or higher)

The AE summaries of Table 5 will be generated with number (%) of participants experiencing at least one event. TEAE will be provided for main treatment-emergent period, LTE treatment-emergent period respectively.

Table 5 - Analyses of adverse events

Type of AE	MedDRA levels	Main period	LTE
All TEAE	Overview ^a Primary SOC, HGLT, HLT and PT	✓	✓
	Primary SOC and PT	✓	
	PT	✓	\checkmark
		✓	
TEAE related to IMP as per Investigator's judgment	Primary SOC and PT	✓	✓
TEAE by maximal intensity	Primary SOC and PT	✓	✓
TEAE Grade 3 or higher	Primary SOC and PT	✓	
Treatment emergent SAE	Primary SOC and PT	✓	✓
Treatment emergent SAE related to IMP as per Investigator's judgment	Primary SOC and PT	✓	✓
TEAE leading to permanent discontinuation of intervention	Primary SOC and PT	✓	✓
Bleeding event by grade ^b	Primary SOC and PT	✓	✓
Bleeding events (Intensity Grade 2 or higher) ^b	Primary SOC and PT	✓	✓
Related bleeding events (Intensity Grade 2 or higher) ^b	Primary SOC and PT	✓	✓

28-Nov-2022	
Version number:	1

Type of AE	MedDRA levels	Main period	LTE
Infection (Intensity Grade 2 or higher) ^C	Primary SOC and PT	✓	✓
Related infection (Intensity Grade 2 or higher) $^{\it c}$	Primary SOC and PT	✓	✓
TEAE by age group (<65, >=65 years)	Primary SOC and PT	\checkmark	
TEAE by gender	Primary SOC and PT	✓	
TEAE by concomitant ITP medications (No concomitant ITP medication, CS alone, TPO-RA alone, CS + TPO-RA)	Primary SOC and PT	✓	

a Will include the following AE categories: any AEs, any serious AEs, any AEs leading to death, any AEs leading to permanent intervention discontinuation

Analysis of deaths

Death will be listed.

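### As its periods are defined, Part B pools laboratory and vital-sign abnormality incidence over the 24-week period and a responder-only extension, and specifies no main-period figure

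*SAP*

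**What the plan says.** SAP Part B section 4.7.3.1 sets the rule for laboratory variables, vital signs and ECG: "Analyses according to PCSA will be performed based on the worst value during the treatment-emergent period, using all measurements". The result is a proportion per criterion: "the incidence of participants with at least one PCSA during the treatment-emergent period will be summarized regardless of the baseline level". It is also broken down by baseline status. The same section adds, to the by-visit descriptive statistics, the last value during the on-treatment period.

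Section 4.1 defines both periods. The treatment-emergent period "is any time after the first administration of rilzabrutinib", and "Treatment-emergent (TE) period includes both on-treatment period and post-treatment period". For the on-treatment period: "The on-treatment period includes the main on-treatment period and the long-term extension (LTE) on-treatment period". Section 4.1 also defines a main and an LTE treatment-emergent period, but section 4.7.3.1 names neither.

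For adverse events, section 4.7.2 does make the split: "TEAE will be provided for main treatment-emergent period, LTE treatment-emergent period respectively". Exposure and compliance (4.7.1) and rescue medication (4.4.2) are split in the same way.

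**The concern.** Read with the section 4.1 definitions, section 4.7.3.1 gives one crude proportion per criterion over very unequal follow-up. A participant who does not enter the LTE contributes at most 24 weeks of treatment plus 4 weeks of follow-up. A participant who enters contributes more, by an amount set by enrolment date. Protocol section 4.2 reserves LTE entry for platelet responders, so length of observation also depends on response.

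The last on-treatment value has the same defect. It is Week 25 or earlier for some participants and an LTE visit for others, so its mean change from baseline refers to no fixed time.

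Clinically significant changes in laboratory tests, ECG and vital signs belong to the Part B primary safety endpoint (SAP Part B section 1.2). As specified, the PCSA tables would not cover the same period as the main-period adverse event tables beside them. The crude figure would also move with the date of the cut.

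**Working it through.** The plan states no expected PCSA incidence, so there is no figure of its own to reproduce.

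**1. Which variables are exposed to the problem.** Protocol Appendix 5 (first six LTE months) and Appendix 6 (thereafter) schedule serum chemistry, haematology, urinalysis, vital signs and weight at each 28-day LTE visit, then every three months. Platelet counts drop out, because section 4.7.3.1 excludes efficacy parameters from PCSA summaries. Single ECG, haemolysis panel, mean platelet volume and immunoglobulins appear in Appendix 5 only at the Day 169 rollover visit, and Appendix 6 has no row for them. Only unscheduled measurements could add to those counts. Coagulation is left out here: Part A's copy of the LTE schedules limits it to following up bleeding events.

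**2. How long the LTE can be at the cut.** Section 4.7.1 gives the exposure cut-off as the last participant's last visit in the 24-week period. First enrolment was 18 February 2021 and the SAP is dated 28 November 2022, 648 days apart. If the cut were at the SAP date (an assumption), the earliest enrollee could have 648 − 168 = 480 days, about 69 weeks, of LTE. Later enrollees would have less.

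**3. Illustration by visit.** Assume a 2% chance of a given PCSA at each roughly monthly assessment, independent between visits.

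- Not entering the LTE, 6 main visits and 1 follow-up: 1 − 0.98^7 = 13.19%.
- Entering, main period only, 6 visits: 1 − 0.98^6 = 11.42%.
- Entering, 6 main, 12 LTE and 1 follow-up: 1 − 0.98^19 = 31.88%.
- Half enter, main period only: 0.5 × 13.19 + 0.5 × 11.42 = 12.3%.
- Half enter, pooled: 0.5 × 13.19 + 0.5 × 31.88 = 22.5%.

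With 35% entering and 6 LTE visits, the pooled figure is 0.65 × 13.19 + 0.35 × (1 − 0.98^13) = 16.7%. With 60% and 14 visits it is 0.40 × 13.19 + 0.60 × (1 − 0.98^21) = 26.0%.

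**4. Illustration by constant hazard.** Assume a 10% risk over 24 weeks, so h = −ln(0.90)/24 per week, and incidence 1 − exp(−h·t). Non-entrants have t = 28 weeks. Entrants have 24 for the main period alone, or 24 + LTE weeks + 4 when pooled.

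| Share entering LTE | Main period only | Pooled, 24 LTE weeks | Pooled, 52 | Pooled, 69 |
|---|---|---|---|---|
| 22% | 11.2% | 13.5% | 15.5% | 16.6% |
| 40% | 10.9% | 15.1% | 18.8% | 20.8% |
| 60% | 10.6% | 16.9% | 22.4% | 25.4% |

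With assumed 24-week risks from 5% to 20%, pooled divided by main-only runs from about 1.2 to 2.5. The 69-week column gives every entrant the longest possible LTE, so it is an upper end.

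**5. Scale in people.** With 23 participants, 12.3% is 2.8 people and 22.5% is 5.2: about three against five.

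**The case against.** The best reply is that a by-period reading is available. Section 4.1 divides the treatment-emergent period into main and LTE parts straight after defining it. Section 4.7.2 defines treatment-emergent adverse events over the same unqualified period, yet tabulates them by period. In Appendix 4, the combined ALT and bilirubin criterion is to be counted within one treatment phase. So a reader who infers that no 24-week incidence will be produced goes beyond the text. What can be said is that none is specified. But for adverse events the split is written down, and the phase remark covers one Appendix 4 row. The defined terms, applied as written, pool.

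It can also be said that main-period data are not lost. By-visit statistics up to Week 25 are planned, and protocol section 10.10.2 describes shift tables by monthly visit and individual listings. That is true, but a by-visit summary does not give the proportion ever abnormal. Section 4.7.3.1 also marks urinalysis, temperature, respiratory rate and several red-cell indices for PCSA-type tables only.

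Three further inferences are tempting and not supported.

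- That ECG abnormality incidence rises with LTE time: no ECG is scheduled in the LTE after Day 169.
- That follow-up in this analysis is unlimited: the LTE itself is open-ended, but the data end at database lock, so LTE time is variable and bounded.
- That the pooling is what prevents comparison with Part A: Part A has no PCSA analysis, and its vital-sign and ECG rules differ. Mainly the liver-enzyme and bilirubin multiples correspond. Part A is useful only as a precedent for naming the period: "There are primarily 3 analysis periods for safety analyses", and its last on-treatment value is the "Last post-baseline visit during the main on-treatment period including unscheduled visits within each dose level".

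Finally, the analysis is descriptive, single-arm and small, and the magnitude rests on assumed inputs. That stands, and it limits the weight of the point.

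**Conclusion.** The point holds for chemistry, haematology other than platelets, urinalysis, vital signs and weight, and for the last on-treatment value of variables still measured in the LTE. As defined, the periods in section 4.7.3.1 combine 24 weeks of treatment with a responder-only extension of varying length, and no main-period PCSA incidence is specified. That an at-least-one proportion cannot fall with added follow-up needs no assumption.

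The size does. About 11% to 13% over the main period against roughly 14% to 26% pooled rests on assumed per-visit or 24-week risks, LTE-entry shares of 22% to 60%, and LTE lengths of 24 to 69 weeks or 6 to 14 visits. Both models assume unchanged risk and ignore clustering. If abnormalities recur in the same people, the rise would be smaller. The figures show direction and rough scale and are not a forecast.

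This is a cheap improvement to the SAP, not a flaw that undermines the safety analysis.

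**What to change.** In SAP Part B section 4.7.3.1, state that PCSA incidence is given for the main treatment-emergent period in the safety population, and separately for the LTE treatment-emergent period in participants dosed in the LTE. State likewise that the last on-treatment value is taken within the main on-treatment period and, separately, within the LTE on-treatment period. Section 4.1 already holds the definitions, and the split matches the one used for adverse events. A combined table may be kept in addition, preferably with length of follow-up or an exposure-adjusted rate beside it.

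The cost is a sentence or two of SAP text and one extra column or table per panel, with small numbers in the LTE column. No new data are needed.
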